13.2.1 SUMMARY OF BASELINE DATA AND FLOW OF PATIENTS

Not applicable

13.2.2 PRIMARY AND SECONDARY ENDPOINT ANALYSIS

The analysis of Phase 1 of the study will be **descriptive** in nature in case it will be not possible identify patients on AnMach from the charts. There will not be statistical comparison between patients identified as being ventilated by anaesthetic machines and those identified as being ventilated by conventional ITU ventilators. The study will not be sufficiently powered to measure a statistical significance of primary and secondary outcomes between the two cohorts of patients.

13.3 THEMATIC ANALYSIS PLANS

A thematic analysis of the interviews will be conducted in order to identify common themes and patterns among the professionals' responses. Thematic analysis has the advantage to condense data into workable themes and the research topics can be explored and interpreted in a way that is not achievable through quantitative data collection only (Castleberry and Nolen, 2018). This kind of analysis allow to examine the perspective of the participants highlighting similarities and differences and summarising unexpected findings (idem). Following a thematic analysis process, the text of transcribed interviews will be coded (every sentence or part of it is assigned a code that identified its meaning) and codes will be grouped in categories and sub-categories. This process will be repeated with all interviews and codes and categories will be revised when new information made it necessary. The final categories will be merged into themes.

13.3.1 Phase 2 ENDPOINTS

The interviews phase aims to detect the proportion of interviewees who experienced difficulties of managing patients with an AnMach and feeling stressed or overwhelmed by the situation.

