6.2 OBJECTIVES

- To collect quantitative data from the charts of patients admitted to 2NA/main recovery from the 1stApril 2020 to the 30th October 2020.
- To survey ITU staff in order to identify professionals that manage patients ventilated via anaesthetic machines.
- To interview consenting professionals that rotated in 2NA/main recovery in the study period: 3 to 5 nurses, 3 to 5 physiotherapists, 3 to 5 doctors trained in Intensive Care, and 3 to 5 consultant physicians (ITU staff but not trained in anaesthesia).
- To perform statistical and thematic analysis of data.
- To prepare a report for HRA and the RFH Research and Development (R&D) Department, dissemination of study results to participants and appropriate stakeholders, preparing manuscript for publication into an Intensive Care/Anaesthetic journal.

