8.1.1 INCLUSION CRITERIA

- ITU professionals (nurses, physiotherapists, ITU consultants trained in intensive care and who that are not accredited anaesthetists) who agree to be interviewed and manifest their consent responding to the survey;
- ITU professionals who managed patients ventilated using anaesthetic machines at the RFH ITU between the 1st April and the 30th of October 2020;

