9.2 PHASE 2 PROCEDURES: qualitative study, survey and interviews

9.2.1 PARTICIPANT RECRUITMENT PROCESS

All participants who wish to enter the study will be fully screened and consented by the Chief Investigator, or one of the qualified clinicians involved in the study as Clinical Co-investigator.

The Survey

A structured questionnaire will be developed by the study team. The questionnaire will be hosted by the Qualtrics platform (<https://www.qualtrics.com/uk/>), a service provided to academics with a stricter privacy policy compared to more frequently used survey platforms. The survey will be a mean of screening ITU professionals. The participants will be asked to answer the following questions:

Qualification: nurse, physiotherapist, intensivist not anaesthetist, anaesthetist
Years of ITU experience

Did you look after a patient ventilated on anaesthetic machine during your time on 2NA/main recovery?
Have you ever ventilated a patient on an anaesthetic machine before this event?
Were you aware of any guidance for ventilating patients using anaesthetic machines?
Have you experienced any problems with ventilating patients on anaesthetic machine? - if yes please describe
Would you consent to be interviewed about your experience using anaesthetic machines?

The first page of the survey will include information accompanying the questionnaire fully explaining the purpose of the research and what the data collected would be used for.

The in-depth interviews

In the second phase of the study, in-depth interviews with 12 (minimum) to 20 (maximum) ITU professionals will be performed. Study participants who volunteer to be interviewed will be contacted on the phone or via a video call platform (e.g. Zoom or Microsoft Teams) and asked for their availability for a thirty minutes interview. The interview will be recorded and later transcribed. Interviewees will be asked to record their consent before beginning the interview. The topic guide for interviews and the answers to the survey will guide the interviews. The main topic will be the professionals experience of managing a patient on anaesthetic machines: easiness, adverse events, solutions, recording of events, impact on their mental health.

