13.2 STATISTICAL ANALYSIS PLANS

The retrospective (and prospective, if available) data collection:

This is a cohort study with no sample size calculation. The number of patients managed on AnMach and charts available (identified as AnMach Use) will dictate how many cases we will be able to analyse. The statistical analysis will be descriptive and performed with the Microsoft Office Excel data analysis package in case we will not be able to identify the AnMach charts and we will collect only adverse events data and report them as proportions. The clinical outcomes will be described using absolute and relative frequencies (expressed as a percentage) or position indices (average or median) and relative dispersion indices (standard deviation or interquartile range) suitable for the type of variable analysed. If comparison between AnMach patients and ITU ventilator patients will be possible, mean and standard

23

deviation of clinical outcomes for the two groups will be compared (the plan for this analysis will be explained in case of requesting a protocol amendment).

The Survey:

The questionnaire answers will be inserted in an excel spreadsheet and cleaned. Incomplete, inaccurate and missing data will be detected and discussed during interviews. The results will be used to select participants for the second stage and implement the topic guide for interviewing the volunteers. For this aspect of the study the statistical analysis will be descriptive and performed with the Microsoft Office Excel data analysis package. Data will be reported as proportions.

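### The only Phase 2 endpoint is a proportion among 12 to 20 selected interview volunteers: it describes them alone, and the eligibility rule as written would narrow the survey proportions in the same way

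*Protocol*

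**What the plan says.** Section 13.3.1 gives a single Phase 2 endpoint: "The interviews phase aims to detect the proportion of interviewees who experienced difficulties of managing patients with an AnMach". The same sentence goes on to join this with being stressed or overwhelmed. Section 13.3 plans only a thematic analysis of the transcripts, moving from codes to categories to themes.

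On who is interviewed, section 9.2.1 states that "in-depth interviews with 12 (minimum) to 20 (maximum) ITU professionals will be performed" and that they are people who volunteer. Section 6.2 sets quotas of 3 to 5 in each of four groups: nurses, physiotherapists, and two groups of doctors. Section 13.2 says of the survey: "The results will be used to select participants for the second stage". One survey item in section 9.2.1 is "Have you experienced any problems with ventilating patients on anaesthetic machine".

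On who is eligible, the Phase 2 inclusion criteria under section 8.2 (numbered 8.1.1 for a second time) admit ITU professionals "who agree to be interviewed and manifest their consent responding to the survey", and section 8.2 rules out exceptions. Section 9.2.1 nevertheless describes the survey as a screening tool whose last question asks for consent to an interview. Section 10 has the link emailed to ITU staff. Section 13.2 reports survey data as proportions.

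**The concern.** A small, purposively chosen group of volunteers suits a thematic analysis, where the product is a range of experiences. It does not suit a proportion. The natural use of such a figure is to say how common difficulty or stress was among ITU staff, and the rationale in section 5.2 looks to improve care and staff support. The interview sample cannot carry that meaning. Volunteering may depend on experience, the quotas fix the professional mix, and a survey answer on nearly the same subject is known before interviewees are chosen.

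The survey is the better source for a proportion, because it goes to staff generally and already has items on exposure and on problems. The inclusion criterion threatens that source. Applied as written, it puts respondents who decline an interview outside the study, and the survey proportions then rest on interview volunteers too.

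**Working it through.** **1. The plan's own number.** Section 6.2 has four groups of 3 to 5 interviews: 4 × 3 = 12 and 4 × 5 = 20. This reproduces the 12 to 20 in section 9.2.1 and agrees with the maximum of 20 in the study summary (section 3.0). The protocol gives no precision or power calculation for Phase 2, so there is nothing further to reproduce.

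**2. Precision if interviewees were a random sample.** The plan does not claim that they are, so this is a reference only. Exact (Clopper-Pearson) 95% limits for x out of n are the 2.5% quantile of Beta(x, n − x + 1) and the 97.5% quantile of Beta(x + 1, n − x).

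| Count | Proportion | 95% limits |
|---|---|---|
| 6/12 | 50% | 21% to 79% |
| 9/12 | 75% | 43% to 95% |
| 10/20 | 50% | 27% to 73% |
| 15/20 | 75% | 51% to 91% |

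**3. Sensitivity to selection.** Let p be the true share of eligible staff with difficulties, and r the chance of being interviewed with difficulties relative to without (volunteering and selection combined). The expected share among interviewees is p·r / (p·r + 1 − p). The protocol gives neither p nor r; all values are assumptions.

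With p = 0.5:
- r = 0.5: 0.25 / (0.25 + 0.5) = 33%
- r = 1: 0.5 / (0.5 + 0.5) = 50%
- r = 1.5: 0.75 / (0.75 + 0.5) = 60%
- r = 2: 1.0 / (1.0 + 0.5) = 67%
- r = 3: 1.5 / (1.5 + 0.5) = 75%

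With other true shares:

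| p | r = 0.5 | r = 1 | r = 2 | r = 3 |
|---|---|---|---|---|
| 30% | 18% | 30% | 46% | 56% |
| 70% | 54% | 70% | 82% | 88% |

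At r = 1 there is no distortion. Below 1 the figure is too low, and above 1 too high.

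**4. Endpoint against analysis.** Section 13.3 contains no step that yields a numerator. The endpoint joins difficulty with feeling stressed or overwhelmed and does not say whether both are needed. The survey items in section 9.2.1 include problems but nothing on stress, so at present only the interviews reach the second half.

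**5. Eligibility against procedure.** Under the section 8.2 criteria, agreeing to an interview is a condition of being in Phase 2. Under sections 9.2.1 and 10, a member of staff may complete the survey and answer no to the interview question. Section 9.2.2 treats the returned questionnaire as implied consent. Section 13.2 does not say whether decliners' answers count in the proportions. The two readings give different denominators.

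**6. Survey cleaning.** Section 13.2 says: "Incomplete, inaccurate and missing data will be detected and discussed during interviews". That route reaches interviewees only. In section 11 interviews start on 15 July while the survey runs to 31 July, so the two overlap.

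**7. Doctor groups.** Section 6.2 separates "3 to 5 doctors trained in Intensive Care, and 3 to 5 consultant physicians (ITU staff but not trained in anaesthesia"). The section 8.2 criteria name only ITU consultants among doctors, and the survey offers one category for intensivists who are not anaesthetists. The survey therefore cannot tell the two quota groups apart.

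**The case against.** The strongest defence is that the endpoint names interviewees as its denominator. As a description of the people interviewed it is not biased, and no section says that it estimates a share of all staff. A reader might infer that the protocol sets out a biased estimate of how many staff had difficulties. The text does not support that: the fault lies in what the figure can be used for and in making it the endpoint.

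A reader might also infer that people are chosen because they reported problems. Section 13.2 does not say which answers drive selection. Profession, exposure and consent would be enough, and section 6.2 gives the survey's purpose as finding staff who managed these patients. Selection on the problems answer is left open, not stated. Nor must the distortion be upward, since overstretched staff may decline.

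Two other inferences go too far. Section 13.2 says that doubtful answers are discussed at interview, not that survey records are overwritten. And a shortfall to 9 to 15 interviews (3 × 3 to 3 × 5) follows only if one doctor quota cannot be filled, which depends on one reading of a garbled criterion; the stated quotas do sum to 12 to 20.

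It is also fair to say that the thematic analysis and survey proportions are already planned, and that a survey by open email has volunteer bias of its own. What stands is the choice of endpoint and the conflict over eligibility.

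**Conclusion.** The point holds within those limits and should be corrected, although it does not undermine the study. A proportion is a poor sole endpoint for a small, selected interview sample. Under the illustrative assumptions in step 3, selection alone could move a true 50% to anywhere from about 33% to 75%. Sampling variation in 12 to 20 people would leave limits about 45 to 58 percentage points wide around an observed 50% (73 − 27 = 46; 79 − 21 = 58), even with no selection. The protocol supplies nothing to say where in that range, or on which side, the result would fall.

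The conflict between the section 8.2 criterion and sections 9.2.1, 10 and 13.2 needs no assumption; it is in the text. Its consequence is conditional: the survey proportions are restricted to interview volunteers only if the criterion is applied to the survey.

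**What to change.** - **Section 13.3.1:** make the Phase 2 interview output themes by profession. Label any counts as being among interviewees only.
- **Section 13.2:** take the proportion with problems from all survey respondents who looked after a patient on an anaesthetic machine. Give the numbers invited and responding, and acknowledge that non-response bias remains. Base these proportions on answers as submitted, before any interview.
- **Section 9.2.1:** add one survey item on feeling stressed or overwhelmed. State which survey answers are used to choose interviewees.
- **Section 8.2:** make agreement to an interview a criterion for the interview stage only.
- **Sections 6.2, 8.2 and 9.2.1:** reconcile the doctor groups so that quotas, eligibility and survey categories match.

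The cost is rewording and one more question. Section 9.2.1 says the questionnaire is still to be developed, and no extra interviews are needed.

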14 DIRECT ACCESS TO SOURCE DATA

The Investigator(s)/institution(s) will permit trial-related monitoring, audits, REC review, and regulatory inspection(s), providing direct access to source data/documents. Trial participants are informed of this during the informed consent discussion. Participants will consent to provide access to their medical notes.

15 ETHICS AND GOVERNANCE REQUIREMENTS

Before any site can enrol patients into the trial, the Principal Investigator must ensure written permission to proceed has been granted by that Trust Research & Development (R&D). If conducting the study at Royal Free London NHS Foundation Trust, contact the R&D team for any assistance.

The site must conduct the trial in compliance with the protocol as agreed by the Sponsor and, which was given favourable opinion by the Research Ethics Committee (REC) and the Health Research Authority (HRA) where applicable.

The Chief Investigator will be provided (via the Sponsor) with file indexes TMF Index RLFRRDDOC0013 and ISF index RFLRDOC0003 for use with SOP019 'Preparation and Maintenance of the Site File – and SOP054 'Preparation and Maintenance of the Trial Master File'. The CI will be responsible for the maintenance of the TMF and may delegate the responsibility of ISF file maintenance to the PI at each participating site.

It is the responsibility of the Principal Investigator at each site to ensure that all subsequent amendments gain the necessary approval. Refer to R&D OFFICE SOP0016 'Protocol amendments of RFL Sponsored Studies' and R&D OFFICE SOP003 'Reporting amendments'.

Within 90 days after the end of the trial, the CI and Sponsor will ensure that the REC is notified that the trial has finished. If the trial is terminated prematurely, those reports will be made within 15 days after the end of the trial. Refer to R&D OFFICE SOP0030 'Study Close Down'

The CI will supply an End of Study report of the clinical trial to the REC within one year after the end of the trial. The sponsor can provide an End of study Report template RFLRDDOC0005.

15.1 DEFINITION OF THE END OF TRIAL

The end of the data collection will be marked as the Last Data entry point. The end of the study is scheduled as the 30th of November 2020 providing a study commencement date on the 1st of July 2020.

15.2 ANNUAL PROGRESS REPORTS (APRs)

The Chief Investigator will prepare the APR in accordance with the RFL R&D Office's SOP 056 'Annual Progress Reports'. Following review by the sponsor the report will be sent to the REC. The APR is due for submission annually within 30 days of the anniversary date on which the favourable opinion was given by the Ethics committee, until the trial is declared ended.

15.3 PROTOCOL COMPLIANCE

Any Protocol Deviations, Violations will be documented using the deviation reporting form (RFLRDDOC0006), and entered onto the Sponsor's deviation log (RFLRDLOG0005) and processed according to R&D OFFICE SOP 032

The CI will notify the Sponsor immediately of any case where there exists a possible occurrence of a violation of the protocol or a breach of Data protection.

16 FINANCE

The Royal Free Charity has agreed to finance the study assigning the study team £4500. This will support the CI time, the qualitative component (interviewer time, interviews transcription cost), and possibly a research assistant for data collection.

17 PEER REVIEW

This protocol has been or will be peer reviewed before it is authorised for use in accordance with the Sponsor's SOP on Peer Review (SOP 055)

18 PUBLIC AND PARTICIPANT INVOLVMENT

A member of the public was sought to review the study and its aims. The public representative felt that it would be appropriate to investigate the effects of using anaesthetic machines and patients. She was particularly interested in effects of moral injury on members of the ITU staff multi-disciplinary team. She had anticipated that stress levels would have been very high due to using unfamiliar equipment.

She fears a second wave and agrees that this study is important as it may inform further practice should a second peak in infections arise.

We will endeavour to identify a member of the public (possibly an ITU professional external to the group of study participants) to join our management team and help us identify opportunities for dissemination of the results to appropriate stakeholders.

19 INDEMNITY

NHS bodies are liable for clinical negligence and other negligent harm to individuals covered by their duty of care. NHS Institutions employing researchers are liable for negligent harm caused by the design of studies they initiate.

20 IP AND DEVELOPMENT POLICY

Unless otherwise specified in agreements, the following guidelines shall apply: All Intellectual Property Rights and Know How (IP) related to the Protocol and the Trial are and shall remain the property of the Sponsor excluding

- 1) Pre-existing IP related to clinical procedures of any Hospital.
- 2) Pre-existing IP related to analytical procedures of any external laboratory.

All contributors

shall assign their its rights in relation to all Intellectual Property Rights and in all Know How, not excluded above to the Sponsor and at the request and expense of the Sponsor, shall execute all such documents and do all such other acts as the Sponsor may reasonably require in order to vest fully and effectively all such Intellectual Property Rights and Know How in the Sponsor or its nominee.

shall promptly disclose to the Sponsor any Know How generated pursuant to this Protocol and not excluded above and undertake treat such Know How as confidential information jointly owned between it and the Sponsor

Nothing in this section shall be construed so as to prevent or hinder a medical professional from using Know How gained during the performance of the Trial in the furtherance of its normal business activities, to the extent such use does not result in the disclosure or misuse of Confidential Information or the infringement of any Intellectual Property Right of the Sponsor.

21 PUBLICATION AND DISSEMINATION POLICY

Publication: “Any activity that discloses, outside of the circle of trial investigators, any final or interim data or results of the Trial, or any details of the Trial methodology that have not been made public by the Sponsor including, for example, presentations at symposia, national or regional professional meetings, publications in journals, theses or dissertations.”

All scientific contributors to the Trial have a responsibility to ensure that results of scientific interest arising from Trial are appropriately published and disseminated. The Sponsor has a firm commitment to publish the results of the Trial in a transparent and unbiased manner without consideration for commercial objectives.

To maximise the impact and scientific validity of the Trial, data shall be consolidated over the duration of the trial, reviewed internally among all investigators and not be submitted for publication prematurely. Lead in any publications arising from the Trial shall lie with the Sponsor in the first instance.

21.2 BEFORE THE OFFICAL COMPLETION OF THE TRIAL

All publications during this period are subject to permission by the Sponsor. If an investigator wishes to publish a sub-set of data without permission by the Sponsor during this period, the **Funder** shall have the final say.

21.3 UP TO 180 DAYS AFTER THE OFFICAL COMPLETION OF THE TRIAL

During this period the Chief Investigator shall liaise with all investigators and strive to consolidate data and results and submit a manuscript for peer-review with a view to publication in a reputable academic journal or similar outlet as the Main Publication.

- The Chief Investigator shall be senior and corresponding author of the Main Publication.
- Insofar as compatible with the policies of the publication outlet and good academic practice, the other Investigators shall be listed in alphabetic order.
- Providers of analytical or technical services shall be acknowledged, but will only be listed as co-authors if their services were provided in a non-routine manner as part of a scientific collaboration.
- Members of the Steering Group shall only be acknowledged as co-authors if they contributed in other capacities as well.
- If there are disagreements about the substance, content, style, conclusions, or author list of the Main Publication, the Chief Investigator shall ask the Steering Group to arbitrate.

